### **5.4 Participant Withdrawal and Discontinuation of IP**

#### **5.4.1 Reasons for Withdrawal/Discontinuation of IP**

At their own discretion, participants may withdraw from the study at any time and for any reason. Study participants will be withdrawn from the study if consent is withdrawn, and will be considered for study withdrawal for non-compliance, significant protocol violation, NAC intolerance and/or severe adverse events, the development of new medical conditions which prevent the continuation of participation, being uncooperative during the study, or if continuing in the study is in conflict with the best interest of the patient. Any patients with emergent AEs will be followed until the AEs are resolved.

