#### **5.4.2 Data Collection and Follow-up for Withdrawn Participants**

Participants who withdraw from the study will be contacted by the study research team to request a final visit and to follow up any unresolved adverse events. After the early termination visit, no further study procedures or evaluations will be performed, or additional study data collected. Any data collected prior to the withdrawal of consent may be retained and used by the sponsor.

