
A linear mixed model will be used to assess baseline brain GSH as a predictor of change in executive function, processing speed, memory and working memory composite z scores over 24 weeks in patients with mild VCI. A GSH x time interaction will indicate a significant relationship between brain GSH and change in executive function, processing speed, memory and working memory performance over time.

Post-hoc analyses will be used to assess change in 8-ISO/LPH ratio over 24 weeks of treatment between possible and probable mild VCI subgroups using linear mixed models. Between group differences in baseline brain GSH levels will also be assessed using analyses of covariance. Where possible, the primary and secondary hypotheses will also be tested in the probable and possible mild VCI subgroups and compared.

Linear regression will be used to investigate baseline serum S100B as a predictor of baseline brain GSH levels, and if serum S100B at baseline will predict change in brain GSH over a 6-month period. Body fat percentage will be included as a potential confounder in this analysis.

Linear regression will be used to assess association between mitochondrial dysfunction as measured by ccf-mtDNA and oxidative stress markers at baseline and over time. A linear regression model will be used to investigate the association between PIGF, oxidative stress markers at baseline and termination. A linear regression model will be used to investigate peripheral MPO as a predictor of executive function or verbal memory at baseline. Age, use of anti-inflammatory medications and inflammatory and vascular comorbidities will be included as covariates. Measures of mood, cognitive function, and metabolic markers (oxylipins) will be compared between the baseline and follow-up visits, and changes in these measures will be compared between individuals relative to each other in a repeated measures linear regression analyses.

**Safety Outcomes:** Frequency of adverse events between treatment and placebo groups will be compared using chi-square/ Fisher exact tests. In addition, exploratory analyses using logistic regression will be performed to determine predictors of cognitive response to NAC, including demographics and compliance.

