### **7.5 Power Calculation**

Based on a published randomized placebo-controlled trial in patients with probable AD, oral NAC treatment resulted in a significant improvement in executive function in the active treatment group ( $p= 0.008$ ) but not in placebo. Our preliminary analysis of MOVE-IT blinded data ( $n=30$ ) was used to provide an updated estimate of the standard deviation ( $SD=0.55$ ) of executive function Z-scores in our population, controlling for education. Based on this, a sample size of 42 (21 in each group) will provide 80% power, at alpha of 0.05, to detect a medium effect size in a linear mixed model with a hypothesized intra-cluster correlation of 0.1. The sample size calculation was carried out using PASS Version 12 (Kaysville, Utah.). Due to the uncertainties of COVID-19 pandemic, a generous drop-out rate was used. To account for a drop-out rate of 42%, we will inflate the sample size to 60.

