## **8.3 Adverse Event Recording**

Investigations into potential adverse events will be conducted throughout the study (in person during the baseline visit, and at 4, 8, 12, 16, 20 and 24 weeks; and over the phone as shown on Appendix A) using a symptom checklist and will be recorded promptly in the source document. This checklist will include all potential side effects listed on the current product monograph for NAC. All emerging AEs will be noted and followed-up until resolution in a timely manner.

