## **8.4 Type and Duration of Follow-up for Adverse Events**

AEs occurring as of the first administered dose of the investigational product and to a follow up period of at least 32 hours (half life of NAC is 6.25hrs) after the last administered dose, will be collected. AEs recorded during this period will be followed through to resolution, or until the event is assessed as chronic or stable.

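### Adverse events are compared only as raw proportions, with no allowance for shorter observation after withdrawal; the comparison is biased if withdrawal differs by arm for reasons other than the event counted

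*Combined protocol and SAP*

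**What the plan says.** The safety paragraph of Section 7.4 states: "Frequency of adverse events between treatment and placebo groups will be compared using chi-square/ Fisher exact tests". Its only other sentence plans exploratory logistic regression for cognitive response. No section mentions person-time, exposure-adjusted rates, time to first AE, or any handling of unequal AE follow-up.

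Four other places determine how long a patient is observed for AEs.

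- Section 8.4 collects "AEs occurring as of the first administered dose of the investigational product and to a follow up period of at least 32 hours" after the last dose. The 32 hours is a minimum.
- Section 8.3 says: "Investigations into potential adverse events will be conducted throughout the study", with reviews up to week 24.
- Section 5.4.2 requests a final visit from patients who withdraw and then stops: "After the early termination visit, no further study procedures or evaluations will be performed, or additional study data collected".
- Section 5.4.1 adds: "Any patients with emergent AEs will be followed until the AEs are resolved". This covers events already open, not new ones.

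Section 5.4.1 also names "NAC intolerance and/or severe adverse events" among the grounds for considering withdrawal. Section 3.2 hypothesises that safety measures, including AE incidence and drop-outs, will be comparable between arms. Section 7.5 gives the planned loss: "To account for a drop-out rate of 42%, we will inflate the sample size to 60".

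**The concern.** A raw proportion treats every patient as equally observed. Here a patient who withdraws at week 4 can contribute new AEs for about 4 weeks, and a completer for 24. If the two arms lose patients at a similar pace, the shortfall is shared. If one arm loses patients sooner, that arm has less time in which to record events and its proportion is pulled down relative to the other.

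Withdrawal in this trial can depend on treatment, because intolerance is a listed ground. The planned loss is also large enough for the difference to matter. At stake is the comparable-safety hypothesis in Section 3.2: a real excess in the arm with more withdrawals could be reduced or hidden, and neither a chi-square nor a Fisher test would show it.

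**Working it through.** **The plan's figure.** The only related number is the enrolment of 60. Dividing by the retained fraction gives 42/(1 − 0.42) = 72.4, so 73. The stated 60 matches 42 × 1.42 = 59.6. That is a separate issue and does not decide this point. What matters here is that 60 × 0.58 = 34.8, so about 35 patients would complete if 42% were lost.

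**Inputs.** From the documents: 24 weeks of treatment (4.1) and 42% overall drop-out (7.5). Assumed, because the documents give no values: a 24-week AE risk p from 20% to 80%, and exits of 34% placebo versus 50% NAC, or 20% versus 64%. Both pairs average 42%.

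**Model.** Constant AE hazard L = −ln(1 − p)/24 and an independent constant exit hazard M = −ln(1 − d)/24, where d is the fraction leaving by week 24. The proportion observed with an AE is

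L/(L + M) × [1 − exp(−24(L + M))].

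Mean observation time, ignoring AEs, is 24d/[−ln(1 − d)]: 21.5 weeks at 20% exits, 19.6 at 34%, 18.5 at 42%, 17.3 at 50% and 15.0 at 64%.

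**Worked case, p = 40%, equal hazards.** 24L = 0.511.
- Placebo, d = 34%: 24M = 0.416, so 0.511/0.926 × (1 − 0.396) = 33.3%.
- NAC, d = 50%: 24M = 0.693, so 0.511/1.204 × (1 − 0.300) = 29.7%.

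The 3.6-point difference comes entirely from unequal observation.

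**Equal true hazards** (placebo %, NAC %; difference in points; crude risk ratio):

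| 24-week risk | Exits 34% / 50% | Exits 20% / 64% |
|---|---|---|
| 20% | 16.5, 14.6; −1.9; 0.89 | 18.0, 12.8; −5.2; 0.71 |
| 40% | 33.3, 29.7; −3.6; 0.89 | 36.2, 26.1; −10.1; 0.72 |
| 60% | 50.6, 45.5; −5.1; 0.90 | 54.7, 40.5; −14.2; 0.74 |
| 80% | 69.0, 62.9; −6.1; 0.91 | 73.8, 56.8; −17.0; 0.77 |

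With exits of 42% in both arms the difference is zero in every row.

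**True NAC hazard 1.5 times placebo** (risk ratio, NAC to placebo):

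| Placebo risk | Full follow-up | Exits 34% / 50% | Exits 20% / 64% |
|---|---|---|---|
| 20% | 1.42 | 1.27 | 1.02 |
| 40% | 1.34 | 1.21 | 0.99 |
| 60% | 1.25 | 1.15 | 0.95 |
| 80% | 1.14 | 1.08 | 0.92 |

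**What a rate does.** Expected time at risk to first AE is [1 − exp(−24(L + M))]/(L + M). Expected first events divided by this time equals L, whatever M is. Under this model the rate ratio therefore recovers 1.00 or 1.50.

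**Exit caused by the AE.** A simulation of 400,000 patients per arm used p = 40%, background exits of 30% in both arms, and half of first AEs on NAC leading to exit. The any-AE proportion was 34.1% in both arms. A second AE type with the same hazard was recorded in 30.9% on NAC against 34.1% on placebo, so the loss falls on later or other events.

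**The case against.** The strongest objection is that the bias is conditional and may be small. Nothing in the documents shows that exits will differ by arm. Section 7.5 calls its drop-out allowance generous and attributes it to COVID-19, which is not an arm-related cause, and 42 evaluable of 60 implies only 30% loss. Section 6.1.1 sends tolerability problems to a dose decision by the qualified investigator, so intolerance need not mean exit. At 30 per arm the standard error of a difference in proportions is up to √(2 × 0.5 × 0.5/30) = 0.129, about 13 points, well above a 2 to 6 point bias. Drop-outs are themselves a safety measure, so an imbalance would be visible. All of this stands and limits the point to an improvement. It does not remove the gap: seeing an imbalance in drop-outs does not correct the AE comparison, and random error does not offset a systematic one.

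A reader might also infer that AE collection ends when a patient stops capsules. The documents do not support that. The 32 hours is a minimum, Section 8.3 runs checks throughout the study, and Section 6.1.4 keeps non-compliant patients in unless there are safety concerns. Only withdrawal clearly cuts observation short.

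A reader might further infer that NAC would look safer than placebo even if it were worse. That can be constructed. Assume a placebo hazard of 0.05 per week, a NAC hazard 30% higher, 42% leaving each arm, placebo leavers at week 12 and NAC leavers at week 4. The proportion is 0.42[1 − exp(−hw)] + 0.58[1 − exp(−24h)], where h is the weekly hazard and w the exit week, giving 55.4% NAC versus 59.5% placebo. The reversal depends on that timing. With NAC exits at week 6 it is 59.4% versus 59.5%; at week 8, 62.8% versus 59.5%, and NAC correctly looks worse. At 30% drop-out with the week 4 and 12 exits it is 62.2% versus 62.5%. The documents support no such gap in timing, and the construction assumes that exits are unrelated to the AE.

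**Conclusion.** The point holds conditionally. The planned AE analysis ignores unequal observation time in a trial that expects substantial withdrawal and stops collecting data on those who leave. If withdrawal is earlier or more frequent in one arm for reasons other than the AE being counted, that arm's raw proportion understates its risk. The false difference is about 2 to 6 points at assumed exits of 34% versus 50% with equal hazards. At assumed exits of 20% versus 64%, a true 1.5-fold hazard gives a crude risk ratio of 0.92 to 1.02, so the excess is hidden.

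These figures assume constant hazards and exits independent of AEs; the documents supply neither AE rates nor exits by arm. The raw proportions should not be read as biased in every case. Equal exits with equal hazards give no bias, and AE-triggered exits leave the any-AE proportion intact while under-counting later or other AE types. The change is worth making because it is cheap, not because a wrong safety conclusion is shown to be likely.

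**What to change.** In the safety paragraph of Section 7.4, before the data are unblinded:

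- Keep the raw counts and proportions by arm.
- Add AE observation time by arm.
- Add AE rates per person-week over the AE collection period, with the rate ratio and 95% CI.
- Add time to first AE, censored at the end of AE collection.
- Show reasons for and timing of withdrawal by arm.

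Sections 8.3 and 8.4 should also be reconciled on whether AEs are collected in patients who stop capsules but remain in the study, because this defines the end of the collection period and hence the denominator.

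The cost is a few sentences and one extra table, with no new visits. The dates should come from dosing, withdrawal and AE records; the team should confirm that the case report form captures AE onset and the last AE review. There are two limitations. A single rate assumes a roughly constant hazard and can mislead if AEs cluster early, which time to first AE avoids. Censoring at exit may be informative when exit relates to tolerability, which is why the withdrawal table belongs beside it.

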- In patients with mild VCI, the 8-ISO to LPH ratio will be significantly lower in those receiving NAC supplementation relative to those who received exercise intervention alone

Evidence from neuroimaging studies in VCI patients indicated greater severity and progression of white matter lesion burden was associated with greater declines in executive function and processing speed. We will investigate whether baseline WMH severity significantly predicts the cognitive response to NAC.

- In patients with mild VCI, those with lower WMH volume at baseline will demonstrate greater cognitive improvement in response to 24 weeks of NAC treatment

Previous trials have shown that NAC at these doses is well-tolerated in the elderly. We will investigate tolerability of NAC.

- In patients with mild VCI, measures of safety (including incidences of adverse events and drop-outs) will be comparable between treatment with NAC and placebo.

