## 5 PARTICIPANT SELECTION AND WITHDRAWAL

A total of 60 mild VCI patients will be recruited from the CR program at the University Health Network Toronto Rehabilitation Institute.

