
## 7.4 Statistical Analyses

All analyses will be performed using current versions of SPSS and SAS (SAS Institute, Cary, NC, USA). The intention-to-treat analyses will be based on data from all patients who undergo randomization, meet the inclusion criteria for the study, receive the trial medication at least once, and undergo at least baseline observation. Descriptive statistics will be calculated for composite z-scores for executive function, memory, and speed of processing. Categorical variables will be summarized using counts and percentages. Continuous variables will be compared between groups using two sample two sided t-tests (or Wilcoxon rank sum tests for non-normal data), whereas categorical variables will be compared between groups using chi-square analyses or Fisher's exact tests.

Primary Hypothesis: Differences in executive function composite z scores between the groups at 24 weeks will be compared between treatment groups using a two sample two sided t-test. A linear mixed model will be run to compare the rate of change in the executive function measure over time (baseline, 12- and 24-weeks). The linear mixed model is selected as it can accommodate missing data in subjects. The effects of age, sex, BMI, total years of education, VO2 peak, physical activity levels, serum homocysteine, will be included as possible covariates. The same analyses will be repeated with the composite z-scores of the other cognitive domains as repeated variables to test for the effect of NAC treatment on the secondary outcome measures.

Secondary Hypotheses: A linear mixed model will also be used to test the hypothesis that patients with mild VCI treated with NAC will show a greater reduction in 8-ISO/LPH ratio over 24 weeks of treatment. The early to late stage lipid peroxidation marker ratio will be inputted as the repeated variable, and treatment group will be added as a fixed factor. The effects of group by time interaction will be evaluated to indicate significant effects of NAC in reducing oxidative stress markers as compared to placebo. APOE4 genotype status, BMI, VO2 peak, and sex will be added as covariates. Similar analyses will be conducted separately with GPx, GR and GST inputted as the repeated variable. Logistic regression analyses will be performed to examine whether baseline severity of WMH is a significant predictor of cognitive response to NAC treatment at 24 weeks, adjusting for the same covariates.

Exploratory Hypothesis:

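### Safety is hypothesised to be comparable between NAC and placebo, but the plan offers only difference tests, with no margin, interval or criterion that could support comparability

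*Combined protocol and SAP*

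**What the plan says.** Section 3.2 (Secondary Objectives) lists as a hypothesis that "measures of safety (including incidences of adverse events and drop-outs) will be comparable between treatment with NAC and placebo".

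The safety paragraph of section 7.4 names one between-arm comparison for it: "Frequency of adverse events between treatment and placebo groups will be compared using chi-square/ Fisher exact tests". That sentence covers adverse events only. For drop-outs, the applicable text is the general rule earlier in 7.4: "categorical variables will be compared between groups using chi-square analyses or Fisher's exact tests". The same section also plans counts and percentages for categorical variables.

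Neither section gives a margin, an interval for a difference in proportions, or a rule for deciding that the arms are comparable. Section 7.5 sizes the trial for executive function only.

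**The concern.** The hypothesis is one of similarity, while the null hypothesis of both named tests is no difference. Rejecting that null counts against the hypothesis. Failing to reject it leaves the hypothesis unsupported, because the same result arises when the arms are alike and when the sample is too small to separate them. Counts and percentages show the observed rates but not how uncertain they are.

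At stake is a listed secondary conclusion in a trial whose title names safety alongside efficacy. As written, the plan has no route by which the data could support that conclusion, and no statement of how large an excess risk would remain possible.

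**Working it through.** **Inputs**
- Total sample: "A total of 60 mild VCI patients will be recruited from the CR program" (section 5).
- Allocation: taken as 1:1 from section 7.5, "a sample size of 42 (21 in each group) will provide 80% power, at alpha of 0.05, to detect a medium effect size". So 60/2 = 30 per arm.
- Sidedness: 7.4 states two-sided for t-tests only ("Continuous variables will be compared between groups using two sample two sided t-tests"); carried over to the safety tests as an assumption, at 0.05.
- Event rates: not in the documents. Placebo rates of 5% to 40%, doubled on NAC, are assumptions.

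**The plan's own figure.** There is no safety power figure to reproduce. The total of 60 does follow from section 7.5: 42 × (1 + 0.42) = 59.64, rounded up to 60.

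**Power to detect a true doubling.** For every pair of counts (i, j), the two binomial probabilities are multiplied and summed over the pairs with two-sided p at or below 0.05, by Fisher's test and by uncorrected chi-square, at 30 per arm:

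| Placebo vs NAC (assumed) | Fisher | Chi-square |
|---|---|---|
| 5% vs 10% | 2% | 11% |
| 10% vs 20% | 10% | 19% |
| 20% vs 40% | 30% | 39% |
| 25% vs 50% | 41% | 52% |
| 30% vs 60% | 56% | 66% |
| 40% vs 80% | 85% | 91% |

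With only 21 evaluable per arm, Fisher power is 8% (10% vs 20%), 19% (20% vs 40%), 36% (30% vs 60%) and 65% (40% vs 80%).

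**One worked result: 12/30 on NAC, 6/30 on placebo**
- Fisher p = 0.16.
- Chi-square: pooled rate 18/60 = 0.30; SE = √(0.30 × 0.70 × 2/30) = 0.118; z = 0.20/0.118 = 1.69; p = 0.09.
- Wilson limits: 0.246 to 0.577 for 12/30; 0.095 to 0.373 for 6/30.
- Newcombe lower limit: 0.20 − √[(0.400 − 0.246)² + (0.373 − 0.200)²] = −0.03.
- Newcombe upper limit: 0.20 + √[(0.577 − 0.400)² + (0.200 − 0.095)²] = 0.41.

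Neither test is significant, yet the data are compatible with an excess of up to 41 points.

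**What 30 per arm can estimate.** Approximate 95% half-width = 1.96 × √(2p(1 − p)/30):
- p = 10%: 15 points
- p = 20%: 20 points
- p = 30%: 23 points
- p = 42%, the drop-out rate assumed in 7.5: 1.96 × √(2 × 0.42 × 0.58/30) = 0.25, or 25 points

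**Would a margin test be feasible?** With equal true rates, one-sided 0.025 and 80% power, n per arm = (1.96 + 0.84)² × 2p(1 − p)/margin². Ruling out a 10-point excess needs 142 per arm at a 10% rate, 252 at 20% and 330 at 30%. Sixty patients support estimation, not a formal comparability claim at a tight margin.

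**The case against.** The strongest reply is that the documents nowhere say a non-significant test will be read as comparability. Section 3.2 states an expectation within an aim to investigate tolerability, and 7.4 says only that frequencies will be compared. That is correct. A reader might infer that a doubling of adverse events would be reported as comparable, but the text contains no such decision rule. What stands is narrower: no criterion is given at all.

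A second reply is that a doubling need not be missed. This also stands in part. Without event rates in the documents, the claim depends on an assumption. From a placebo rate of about 30% upward, either test would detect a doubling more often than not, and an any-adverse-event rate elicited by repeated symptom checklist (section 8.3) could be that high. Chi-square, which the plan also names, has more power than Fisher.

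Third, counts and percentages by arm would let a reader see 40% against 20% beside the p-value. True, but they carry no measure of uncertainty.

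Finally, low power for adverse events is normal in a 60-patient phase II trial. That would answer the point if safety were only described. Here comparability is a stated hypothesis.

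**Conclusion.** The point holds in this form: the planned difference tests cannot support the comparability hypothesis, and the plan supplies no margin, interval or criterion that could. That conclusion rests on the text and on no assumed rate.

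The size of the problem does rest on assumptions: 30 evaluable per arm, two-sided 0.05, and illustrative event rates. On these, a true doubling is often missed for placebo rates up to about 20–25% (Fisher power 30% and 41% at those two rates). It is more likely to be found than missed from about 30%, although Fisher would still miss it in 44% of trials at 30% vs 60%. The stronger readings, that the plan commits to treating non-significance as comparability or that any doubling would usually go unnoticed, are not supported.

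The primary efficacy analysis is unaffected. This is a worthwhile correction to a secondary conclusion.

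**What to change.** In section 7.4:
- Make the risk difference (NAC minus placebo) with a 95% confidence interval, by Newcombe or a similar method, the main safety summary for any adverse event, serious adverse events, adverse events leading to discontinuation, and drop-out. This also gives drop-outs an explicit analysis.
- Word the conclusion as the excess risk that the upper confidence limit rules out.
- State that a non-significant chi-square or Fisher test will not be taken as evidence of comparability.

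The cost is a few lines of analysis-plan text and one table, with no extra patients or data. The downside is that the wide intervals will look less reassuring than a bare p-value. A powered non-inferiority test is not proposed, given the sample sizes it would need.
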